7. INFORMED CONSENT PROCESS

A student researcher will facilitate the informed consent process with the eligible participants once participants have agreed to take part in the study. The informed consent process will take place in a designated private room at Loma Linda University School of Allied Health Professions and in a private classroom at Stanbridge University with time allotted for questions from the participant. HIPPA compliance forms will be included in the informed consent process and a copy of the participants' Bill of Rights. All research records will be secured by placing them in a locked cabinet in a locked office of the principal investigator and/or student researcher.

8. STUDY DESIGN

a. Background or rational for this study

Carpal tunnel syndrome, a common neuropathy of the median nerve may be caused from an increased pressure of the carpal tunnel, prolonged exposure to hand-arm vibrations, a combination of repetitive hand use or hand force, and in recent years has expanded to include the use of computers and similar devices (Ali, Battecha, & Mansour, 2013). It is believed chronic repetitive use of the fingers and wrist may generate a shearing between the carpal tunnel, the median nerve, and the flexor tendons.

Carpal tunnel syndrome is the most frequent type of injury and makes up 41% of all identified upper extremity musculoskeletal disorders (Roll, 2016; United States Department of Labor, 2015). Annually \$15 – 18 billion dollars are spent in costs related to upper extremity musculoskeletal disorder and carpal tunnel syndrome (United States Department of Labor, 2015). Commonly related to repetitive work exposures, prevalence increases with age and is three to one more prevalent in females. The targeted population of carpal tunnel syndrome is highly associated with overuse of the upper extremities (Thomsen, Gerr, & Atroshi, 2008).

Individuals who work in highly repetitive work environments have a significant chance of being diagnosed with carpal tunnel syndrome. Jobs in manufacturing, the service industry, and nursing are identified among this population. However, evidence now includes office workers as Coggon et al. (2013) found individuals who use computers for four hours a day also experience a high incidence of carpal tunnel syndrome. Goldfarb (2016) furthered the Coggon et al. (2013) study with findings that those who use computers and work 12-hour days over an eight-year span are primarily the at-risk population, putting students at the highest risk.

According to the Occupational Therapy Practice Framework, it is within Occupational Therapy's domain to intervene in musculoskeletal disorders as it impairs body function. Established treatment strategies for carpal tunnel syndrome include surgical interventions and non-surgical interventions; however, in a systematic review, Roll & Hardison (2017) found no standardized protocol exists for management and treatment of carpal tunnel syndrome. Both surgical and non-surgical interventions have been found to have similar results and governmental regulation, along with decreased reimbursement are putting demands on early worksite intervention (Lysaght et al., 2010). The most common accepted non-surgical protocol for carpal tunnel syndrome include lumbrical stretching exercises and a general cock-up splint, with one study reporting symptom relief up to 24-weeks (Baker et al., 2012; Manente et al., 2012). None of the accepted protocols take into consideration new evidence that suggests the wrist positioned in neutral and fingers supported in extension, provides the best outcomes for individuals with carpal tunnel syndrome (Bulut et al., 2015), and leaves the issue of splint compliance unaddressed. Clearly, a new intervention for carpal tunnel syndrome is needed.

Kinesio Tape is transitioning from the sports arena into rehabilitation as a modality for pain, increased activation of the lymphatic system, as an endogenous analgesic, and to correct musculoskeletal alignment (Kase et al. 1998). Fourteen peer-reviewed studies had been conducted for lower extremity pain and function, with few studies of Kinesio Tape on the upper extremities. Common application protocol for carpal tunnel syndrome is on the flexor side of the wrist and hands. The Kase accepted method of application to the flexor surface of the wrist has face validity only. To the best of our knowledge there are no studies that exist on the dorsal application of Kinesio Tape to facilitate wrist neutral and finger extension.

The primary purpose of this randomized controlled trial graduate student research study is to explore the effect of dorsal application of Kinesio Tape on occupational performance as measured by pain, strength, and function of individuals with carpal tunnel syndrome forearm wrist hand pain as compared to the usual and accepted most common non-surgical intervention of lumbrical stretching exercises and general cockup splint. The secondary purpose is to explore changes in occupational performance through semi-structured interviews in order to understand if Kinesio Tape contributed to results and if so, how. In order to help us understand how the participants perceived the interventions, the third purpose is to explore concepts of adherence to interventions with carpal tunnel syndrome.

b. Objectives

1. Determine if the dorsal application of Kinesio Tape applied to the wrist extensors for individuals with carpal tunnel syndrome and forearm wrist hand pain makes a difference in occupational performance as measured by pain, strength, and function.
2. Explore the perspectives of participants to understand if Kinesio Tape contributed to changes in occupational performance, and if so, how.

3. Explore concepts of adherence to interventions with carpal tunnel syndrome.

c. Procedures involved (Research Interventions)

The following procedures will be used for this multi-method study design that consists of a randomized control trial and descriptive qualitative study, upon IRB approval:

1. Recruit via snowballing, word-of-mouth, flyers, emails, and social media (See Appendix A)
2. Respond to study interest via Phone Script to answer questions regarding the study (See Appendix B) and set up a meeting time to review consent and initiate study procedures.
3. Review Informed Consent, HIPPA documents, and Patient's Bill of Rights and obtain consent from those interested in participating in study.
4. Screen participants for inclusion criteria by administering the Phalen's Test or Tinel's Test (Appendix C).
5. Administer Demographic questionnaire (Appendix D).
6. Administer baseline Week One Visit One Boston Carpal Tunnel Questionnaire, Numeric Pain Rating Scale, Visual Analogue Scale (Appendices E – F - G). If participant has symptoms in both extremities, the researcher will use each extremity as a separate unit and apply corresponding intervention to both extremities.
7. Collect Week One Visit One Baseline Grip and Pinch measurements (Appendix H).
8. Randomly assign participants using a random number generator, to one of three groups:
Intervention group, control group, or usual protocol group. A script will be used to control for bias and ensure consistency between groups.

Intervention group:

The student researcher and/or student research assistants who have been trained in Kinesio Tape and application procedures will apply the baseline dorsal application of Kinesio Tape according to determined protocol. The Kinesio Tape will be measured along the participant's lateral epicondyle to metacarpophalanges, the Kinesio Tape then bifurcated. Anchor Kinesio Tape on the dorsal side at the musculotendinous juncture to digits 1 and 5, just past the carpalmetacarpophalangeal joint of digit 1 and metacarpophalange of joint 5, wrist in flexion to stretch the skin, paper off tension (10%). Kinesio Tape application to digits 1 and 5 with carpalmetacarpophalangeal and metacarpophalange flexion during application. Two space correction pieces

applied to both the extensor and flexor surface at 75% stretch, then radially deviate, smooth edges, ulnarly deviate, smooth edges, repeat.

A handout with Kinesio Tape Removal Instructions will be provided (Appendix I). A symptom journal will be provided with instructions to complete daily (Appendix J). A script will be used with participants (Appendix K).

Control group:

The student researcher and/or student research assistants will apply the Sham application of Kinesio Tape, a four-inch strip of Kinesio Tape to the participants' shoulder (scapular spine). A handout with Kinesio Tape Removal Instructions will be provided (Appendix I). A symptom journal will be provided with instructions to complete daily (Appendix J). A script will be used with participants (Appendix K).

Usual protocol group:

The student researcher and/or student research assistants will provide a general wrist cock up splint with instructions to wear nightly and record compliance in a Splint and Exercise journal (Appendix L). Wrist Lumbrical exercises will be demonstrated by the student researcher or student research assistants and a handout with instructions provided (Appendix M). A symptom journal will be provided with instructions to complete daily (Appendix J). A script will be used with participants (Appendix K).

9. Week One Visit Two a student researcher and/or student research assistants will remove Kinesio Tape, check splints, and collect symptom journals and the Usual protocol group Splint-wearing and Exercise journal. Participants will complete Boston Carpal Tunnel Questionnaire, Numeric Pain Rating Scale, Visual Analogue Scale. Grip and Pinch measurements will be recorded.

Student researcher and/or student research assistants will re-apply Kinesio Tape and check splint and exercises resumed with the Usual protocol group.

Total exposure to application and removal of Kinesio Tape is four times as participants return every third day of Weeks One and Two.

10. Week Two Visit Three a student researcher and/or student research assistants will remove Kinesio Tape, check splints, and collect symptom journals and the Usual protocol group Splint-wearing and Exercise journal. Participants will complete Boston Carpal Tunnel Questionnaire, Numeric Pain Rating Scale, Visual Analogue Scale. Grip and Pinch measurements will be recorded.

Student researcher and/or student research assistants will re-apply Kinesio Tape and check splint and exercises resumed with the Usual protocol group.

11. Week Two Visit Four a student researcher and/or student research assistants will remove Kinesio Tape, check splints, and collect symptom journals and the Usual

protocol group Splint-wearing and Exercise journal. Participants will complete Boston Carpal Tunnel Questionnaire, Numeric Pain Rating Scale, Visual Analogue Scale. Grip and Pinch measurements will be recorded.

Student researcher and/or student research assistants will re-apply Kinesio Tape and check splint and exercises resumed with the Accepted protocol group.

12. Week Three Visit Five a student researcher and/or student research assistants will remove Kinesio Tape, check splints, and collect symptom journals and the Usual protocol group Splint-wearing and Exercise journal. Participants will complete Boston Carpal Tunnel Questionnaire, Numeric Pain Rating Scale, Visual Analogue Scale. Grip and Pinch measurements will be recorded.
13. Up to 26 participants from the Intervention group will be invited to participate in a 30-minute semi-structured audio-recorded interview with student researcher (Appendix N).
14. Email Reminder Script regarding study date (Appendix O)
15. See Timeline (Appendix P)

- d. Concise review of literature that supports the rationale, objectives, and methodology of the proposed study.

An upper extremity musculoskeletal disorder affect working populations worldwide with evidence indicating 20% - 30% experience symptoms, and is considered the second most common cause of worldwide disability (Luckhaupt et al., 2013; Murray et al., 2012; 2013). In the United States alone, upper extremity musculoskeletal disorders are the second most common diagnosis, just behind low back injury for missed days of work, and accounted for 34% of all work-related injuries in 2015, according to the U.S. Bureau of Labor Statistics (2015), but less than 2% of the national Institute for Health budget is allocated to musculoskeletal disorders (Weinstein, 2016). Occupational performance is the process of assisting clients in becoming actively engaged in their life activities while developing healthy behaviors and minimizing costs (Baum & Law, 1997). An upper extremity musculoskeletal disorder impairs an individual's ability to work, complete daily self-care tasks of both gross and fine motor (United States Bureau of Labor Statistics, 2015).

The most common musculoskeletal disorder of the upper extremity is Carpal Tunnel Syndrome and is 41% all off upper extremity repetitive movement disorders (Roll, 2016). Occupational therapists historically have had a role in treating upper extremity musculoskeletal disorder conditions and holistically address the link between reductions in impairment to functional tasks (Roll, 2017). According to Roll (2017) studies of the upper extremity have evaluated orthosis and modalities to increase body structure and occupation as specific interventions for upper extremity musculoskeletal disorder of carpal tunnel syndrome; however, there is a lack of homogeneity within publications. Musculoskeletal disorders and carpal tunnel syndrome are often treated by occupational therapists but in

separate departments (Roll, 2017), which cause problems for researchers and injured individuals alike. Traditionally Occupational Health Occupational Therapists provide interventions to individuals injured at work, often pre-surgically while Hand Occupational Therapists report treating individuals with carpal tunnel syndrome post-surgically. These distinctions carry over into publications and research, though interventions and outcomes are the same.

Diagnosis of carpal tunnel syndrome is confirmed through electromyography; however, medical personnel including Occupational Therapists assess carpal tunnel syndrome based on signs and symptoms and through an orthopedic special test known as the Wrist Flexion Test or the Phalen's Test. Evidence suggests Phalen's Test and Tinel's Test to be valid with high specificity, validity, and reliability. Denham et al. (2015) reported that specificity of the Phalen's Test was 80% with confirmed diagnosis of carpal tunnel syndrome. Other studies indicate that the sensitivity of the Phalen Test and electromyography between 68% and 85% and 73% to 89%. Kotevoglu & Gulbahce-Saglam (2005) found that there was a correlation of ($r = 0.80, p < 0.001$) for the Phalen Test using diagnostic ultrasound and Tinel's Test correlation factor of ($r = 0.70, p < 0.001$). No standardized protocol for management and treatment of carpal tunnel syndrome exists; however, common established strategies consist of surgical or non-surgical interventions. Surgical interventions are mostly positive but a recent study by Nanavati, Walker-Bone, Stanworth and Williams (2013) found almost one-third reported difficulty completing activities of daily living or experienced a return of symptoms 28 days or more following surgery.

Non-surgical interventions lack established uniform protocol according to a systematic review by Amini (2011), and Oiyun and MacDermid (2011) found an analysis of conservative approaches plateaued in effectiveness after three months. The most common non-surgical intervention is splinting with evidence for either full-time or night depending on protocol and patient compliance with only mediocre effectiveness (Amini, 2011). Recent evidence indicates finger position can influence properties of the median nerve with significant palmar bowing of the flexor retinaculum for finger extension and a flattening of the median nerve during the isometric squeeze grip (Nadar et al. (2013). Bulut et al. (2015) found evidence that the wrist positioned in neutral and metacarpophalanges supported, provides the best outcomes, but is yet to be seen in clinical practice. One non-surgical intervention transitioning from Sport Medicine into Rehabilitation is Kinesio Tape.

Kinesio Tape is applied to the epidermis of the skin and by compression released on the nociceptors (pain receptors) provides input through the subcutaneous tissue layer to the body's proprioceptive system according to Kase, Hashimoto and Okane (1998). This hypodermic input influences pain, edema, and is able to provide musculoskeletal correction based on application (Kase et al, 1998). Application ranges from injury management to muscle facilitation and include neurologic impairment interventions as well. Brateanu (2009) elaborated on Kinesio Tape's ability to be worn for several days, three to five, without reapplication and evidence of common applications for patellar pain syndrome, low back pain, and shoulder instability. Few studies exist on upper extremity use of Kinesio Tape on forearm, wrist, hand pain and function, such as with carpal tunnel syndrome. The Kase accepted method of Kinesio Tape application is on the flexor surface for musculoskeletal

disorder of carpal tunnel syndrome symptoms but has face validity only. Kocjan (2016) in a randomized control trial of Kinesio Tape on the flexor side for carpal tunnel syndrome using a non-Kase method of application concluded no statistical significant results. To the best of our knowledge no literature exists on the dorsal application of Kinesio tape for positioning the wrist in neutral, with the finger supported. The process of exploring the effects of Kinesio Tape on musculoskeletal disorders includes understanding participant's issues of compliance as it relates to pain and non-surgical interventions.

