5. INCLUSION/EXCLUSION CRITERIA

INCLUSION

- Adults > 18 years of age
- Fluent in English
- Report signs and symptoms of carpal tunnel syndrome
- Pain, numbness, and tingling of the forearm, wrist, or hand, which worsen at night
- Demonstrate positive Phalen's Test or Tinel's Test of the affected extremity

EXCLUSION

- Currently receiving treatment for carpal tunnel syndrome
- History of surgical carpal tunnel release
- Pregnant
- Diabetes not controlled by medication
- Radiculopathy ie: cervical radiculopathy, diabetic radiculopathy
- Thoracic outlet syndrome
- Allergy to adhesives or compromised skin integrity
- Past history of traumatic event, surgery, or congenital impairment of the forearm, wrist, or hand

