11. DATA ANALYSIS

The research analysis plan will include a repeated measures multi-factorial analysis of variance to analyze continuous data for the functional grip and pinch measurements, with an analysis of covariance to rule out any confounding variables between groups. For Objective 1 of the randomized controlled trial of the study continuous data will be analyzed with change score analysis from baseline to end of study. To compare groups post-hoc Bonferroni will be used. Non-parametric statistics using the Friedman's Test will be used with the Numeric Pain Rating Scale, Visual Analogue Scale, and Boston Carpal Tunnel Questionnaire.

For Objective 2, qualitative data will be analyzed for thematic coding. Transcripts will be individually read and coded for emerging themes by the research team and then analyzed as a group to increase rigor. For Objective 3 to explore concepts of adherence to interventions with carpal tunnel syndrome, triangulation will be used with data obtained through interviews and with journals using a deductive approach to explore Kinesio Tape on performance. Data will be analyzed until redundancy is achieved.

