14. COMPENSATION

Participants will receive a \$5.00 gift card per visit for each of the five visits for the study.

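### The Visit One steps put the provocation test before baseline pain and function with no stated rest, so any lingering provoked symptoms would count as improvement in the over-time tests

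*Combined protocol and SAP*

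**What the plan says.** Section 5 makes a positive provocation test a condition of entry: "Demonstrate positive Phalen's Test or Tinel's Test of the affected extremity". Section 8(c) gives the order of work. After enquiry, staff "set up a meeting time to review consent and initiate study procedures" (step 2), and consent is step 3. The next steps are:

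- Step 4: "Screen participants for inclusion criteria by administering the Phalen's Test or Tinel's Test (Appendix C".
- Step 5: "Administer Demographic questionnaire (Appendix D".
- Step 6: "Administer baseline Week One Visit One Boston Carpal Tunnel Questionnaire, Numeric Pain Rating Scale, Visual Analogue Scale".
- Step 7: "Collect Week One Visit One Baseline Grip and Pinch measurements (Appendix H".
- Step 8: random assignment to three groups.

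No rest between steps 4 and 6 is mentioned. Section 14 pays participants "per visit for each of the five visits for the study", and no separate screening visit is described. Steps 9 to 12 (Visits Two to Five) collect the same outcomes and do not list Phalen's or Tinel's Test.

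In Section 11, grip and pinch are the outcomes named as continuous, and for Objective 1 "continuous data will be analyzed with change score analysis from baseline to end of study". For the Numeric Pain Rating Scale (NPRS), Visual Analogue Scale (VAS) and Boston questionnaire, the only test named is Friedman's.

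**The concern.** A positive Phalen's or Tinel's Test means that the manoeuvre has just reproduced symptoms. On the numbered order, every enrolled participant then gives baseline pain and function scores with no stated recovery time, whereas no later score follows a provocation. If some of the provoked pain is still present at step 6, the baseline is recorded in a more symptomatic state than the visits it is compared with. The return to the usual state would then appear as improvement, in the sham arm as in the others.

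Pain and function are two of the three components of Objective 1. Their named test asks whether scores differ across visits, and a shift confined to the first visit is one of the things it detects. The size of improvement reported within each arm would be overstated by the same amount. Once baseline has been collected this way it cannot be repaired, because no pre-test value exists.

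**Working it through.** **Plan's own figures.** Section 6 gives 64 needed, 20% attrition, 78 in total and 26 per arm. 64 x 1.2 = 76.8, so 77, and the next multiple of three is 78. 64 / 0.8 = 80. The point does not depend on which was used. With 20% attrition an arm of 26 falls to 26 x 0.8 = 20.8, about 21.

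**Order of steps.** Test (4), demographic form (5), questionnaires (6), strength (7), randomisation (8). A carry-over from step 4 can reach steps 6 and 7. It arises before assignment, so its expected size is the same in all arms.

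**Within-arm Friedman's Test, in points.** The documents give no carry-over size and no SD, so these are assumptions:
- no true change over five visits, scores rounded to 0-10, two-sided 5% level
- NPRS mean 4.5, between-person SD 1.5, visit-to-visit SD 1.5
- carry-over at baseline only, with SD equal to half its mean

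Simulated rejection rates:

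| Mean carry-over | 26 participants | 78 participants |
|---|---|---|
| 0 | 5% | 5% |
| 0.25 point | 6% | 14% |
| 0.5 point | 16% | 44% |
| 1 point | 53% | 98% |
| 1.5 points | 85% to 89% (two runs) | 100% |

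The column for 78 ignores attrition.

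**The same test, in SD units.** Here the carry-over is constant, and the within-person correlation is assumed to be 0.5 or 0.7 (2,000 runs per setting):

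| Carry-over | 26 per arm (0.5 / 0.7) | 21 per arm (0.5 / 0.7) |
|---|---|---|
| 0.2 SD | 12% / 18% | 10% / 15% |
| 0.3 SD | 22% / 35% | 18% / 28% |
| 0.5 SD | 58% / 84% | 48% / 72% |

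The two sets agree. In the first, total SD = sqrt(1.5^2 + 1.5^2) = 2.12 and the correlation is 2.25 / 4.5 = 0.5, so 1 point is 1 / 2.12 = 0.47 SD.

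**Between-arm comparison.** In the same simulations, one-way ANOVA on change from baseline to Visit Five rejects 4% to 6% of the time at every carry-over tried (0 to 0.8 SD). Mean change in each arm moves by about the size of the carry-over, equally in all three.

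**Precision, if NPRS change scores were also computed.** Without carry-over, change-score variance is 2 x 1.5^2 = 4.5. A carry-over with SD b raises it by the factor (4.5 + b^2) / 4.5.
- Mean 0.5, b = 0.25: (4.5 + 0.0625) / 4.5 = 1.014
- Mean 1.5, b = 0.75: (4.5 + 0.5625) / 4.5 = 1.125

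The increase is therefore about 1% to 13%.

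**The case against.** **Persistence is not shown.** Nothing in the documents says that provoked symptoms last through the demographic form to step 6. The recall windows of the NPRS, VAS and Boston questionnaire are in appendices not available here. If they ask about recent days, a brief provocation matters little. This stands, and it makes the point conditional.

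**The timing is inferred.** Only steps 6 and 7 carry the Visit One label. The numbered list is not strictly chronological (the email reminder is item 14, after the final interview), and Section 7 speaks of consenting people who are already eligible. A separate screening is possible. Still, the single meeting in step 2 and the count of five visits make the same-visit reading the natural one, and no text sets an interval.

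**The trial is comparative.** Baseline precedes randomisation, so the between-arm contrast is protected. This also stands. A reader might infer that the order biases the trial towards the dorsal tape. It does not: the expected shift is the same in all arms. But Section 11 names no between-arm test for pain and function, so the protected contrast is not the one planned for those outcomes.

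**Friedman's Test is weak evidence of efficacy anyway.** Natural course or regression to the mean could also make it reject. That is true and is a separate weakness. Reordering removes one avoidable cause, not all of them.

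**Reordering everything could move the problem.** Section 8(d) reports flattening of the median nerve during isometric squeeze grip, so strength testing immediately before the provocation test could affect eligibility. This is a fair objection to moving grip and pinch, and the fix leaves them after the test.

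**Conclusion.** The point holds as a conditional, low-to-moderate threat to the within-arm pain and function results. The step order, the missing rest and the absence of the test at later visits are in the text. The carry-over itself is assumed. Within-arm false positives stay near 5% if it is zero, and rise to about 16% at 0.5 point and 53% at 1 point for 26 participants under the assumptions above. The case is strongest for the NPRS and VAS, and weaker for the Boston questionnaire, whose recall window is not shown.

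Three stronger readings are not supported:
- **A certain bias in all outcomes.** Persistence to step 6 is not documented, and nothing says that the test lowers grip or pinch.
- **A biased treatment comparison.** Between-arm tests of change stay at about 5%.
- **A large loss of precision.** A 22% rise in change-score variance needs a carry-over SD of 1, since (4.5 + 1) / 4.5 = 1.22. With SD at half the mean, that is a mean of 2 points, beyond the 0.5 to 1.5 points considered. Within that range the rise is about 1% to 13%.

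**What to change.** Reorder Visit One in Section 8(c):

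1. After consent, complete the NPRS, VAS and Boston questionnaire.
2. Do Phalen's or Tinel's Test.
3. Take a fixed rest, stated in the protocol, and then measure grip and pinch.
4. Randomise those who qualify.

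This removes any carry-over from the baseline pain and function scores, whatever its size, and keeps gripping away from the eligibility test.

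The cost is a few minutes of questionnaires for people who then fail screening, and a short rest. Keep the forms of screen failures under the three-year retention rule in Section 10, but do not analyse them. No extra visits, staff or participants are needed, and the sample size stays at 78.

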12. RISK AND INJURY

Participants may experience discomfort or skin irritation from wearing the tape, splint or completing the exercises. Participants may also experience fear and/or anxiety, and/or hyperventilation before during, or after application of Kinesio Tape, and/or splint, and/or exercises. Under these circumstances the Kinesio Tape will be removed from the participant's forearm wrist hand and provide first aid and seek medical care as needed. To minimize the potential of risks to participants the student researcher and student research assistants will ask if any known allergies to adhesives. Participants with a history or current allergy to adhesives will be excluded from the study. Risks may also include a participant may feel uncomfortable answering questions during interviewing. Loss of confidentiality may occur if two participants know each other. In order to protect confidentiality a number will be assigned to each participant. The master list and Informed Consent will be kept separate in the Principal Investigator's office.

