found finger position can influence properties of the median nerve and Bulut et al. (2015) found the wrist positioned in neutral and metacarpophalanges supported provides the best outcomes. Kase et al. (1998) identified four principles of Kinesio Tape, that it supports muscles by improving muscle contraction, increases flow of body fluids, activates the endogenous analgesic system resulting in decreased pain, and corrects joint alignment based on application. Fourteen peer review studies between 2004 – 2014 provide evidence of KT for lower extremity pain and edema. Few and poor studies exist on upper extremity use of KT, such as with carpal tunnel syndrome and the Kase accepted method of Kinesio Tape application for carpal tunnel syndrome is on the flexor surface (palm of the hand and wrist) but has face validity only. However, if Kinesio Tape is to support or facilitate muscles based on application, as well as provide musculoskeletal re-positioning, and influence sub-acute pain, then using Kinesio Tape on the flexor surface would seemingly only increase compression on the median nerve by pulling the wrist and fingers into flexion/grip position. The application of Kinesio Tape on the extensor surface may reposition the wrist into neutral and open the carpal tunnel while supporting the metacarpophalanges. Thus, the purpose of this study is to determine if the dorsal application of Kinesio Tape applied to the wrist extensors for individuals with carpal tunnel syndrome, makes a difference in occupational performance of pain, strength, and function and to explore the perspectives of participants to understand if Kinesio Tape contributed to changes in occupational performance and compliance and if so, how.

References

American Occupational Therapy Association. (2014). Occupational therapy practice framework: Domain and process (3rd ed.). *American Journal of Occupational Therapy*, 68(Suppl. 1), S1–S48. <http://dx.doi.org/10.5014/ajot.2014.682006>

Amini, D. (2011). Occupational therapy interventions for work-related injuries and conditions of the forearm, wrist, and hand: A systematic review. *American Journal of Occupational Therapy*, 65, 29-36. <http://dx.doi.org/10.5014/ajot.2011.09186>

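### At Visits Two to Five the tape comes off before pain, function and strength are recorded, so no Objective 1 outcome is scheduled with dorsal tape on and only the intervention arm has tape removed from the rated limb first

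*Combined protocol and SAP*

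**What the plan says.** Section 8c puts the baseline questionnaires and strength tests (steps 6 and 7) before randomisation and first taping (step 8), so baseline is off tape in every arm.

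At Visits Two to Five (steps 9 to 12) the listed order is the same each time. Staff first "remove Kinesio Tape, check splints, and collect symptom journals and the Usual protocol group Splint-wearing and Exercise journal". Next, "Participants will complete Boston Carpal Tunnel Questionnaire, Numeric Pain Rating Scale, Visual Analogue Scale". Then "Grip and Pinch measurements will be recorded". Re-application follows at Visits Two, Three and Four; there is none at Visit Five. No interval between removal and measurement is stated and no reason is given for the order. Sections 9 and 11 do not take the matter up.

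The arms differ in where tape sits. In the intervention arm it runs along the forearm to digits 1 and 5, with two further pieces on the extensor and flexor surfaces. The control arm receives "a four-inch strip of Kinesio Tape to the participants' shoulder (scapular spine"). The usual-protocol arm has a splint and exercises and no tape.

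The rationale in Section 16 is largely positional: "The application of Kinesio Tape on the extensor surface may reposition the wrist into neutral and open the carpal tunnel". Objective 1 asks whether dorsal taping makes a difference to pain, strength and function; it does not say whether that means while the tape is worn or after it is off.

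**The concern.** Two things follow from the listed order.

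First, grip and pinch describe the hand at the moment of testing. If the tape works by supporting the wrist and fingers while worn, strength tested after removal does not measure that. A null strength result could be read as showing that the tape does nothing in use, when only the residual effect was tested. The same applies at Visit Five, the endpoint of the change from baseline in Section 11.

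Second, a procedure on the rated limb comes before the ratings in one arm only. The shoulder sham cannot balance it, and the splint arm has no counterpart. Anything that removal does to a pain rating or an effort-dependent grip would enter the comparison between arms as if it were a treatment effect. Neither the participants' ratings nor the analysis can separate the two.

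**Working it through.** The check is a visit-by-visit count from Section 8c, steps 6 to 12.

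| Visit | Tape state when outcomes are listed | Tape applied afterwards |
|---|---|---|
| One | before first application | yes |
| Two | after removal | yes |
| Three | after removal | yes |
| Four | after removal | yes |
| Five | after removal | no |

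**Reproducing the plan's own figure.** Applications: Visits One to Four = 4. Removals: Visits Two to Five = 4. Step 9 states four exposures to application and removal, so the count agrees with this reading of the schedule.

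**Objective 1 outcomes with tape in place.** Visit One is before application and Visits Two to Five are listed after removal: 0 of 5.

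**Visits where tape is taken from the rated limb before outcomes are listed.**
- Intervention arm: 4 of 5, that is, every post-baseline visit.
- Sham arm: 0 of 5 (the 4 removals are at the shoulder).
- Usual-protocol arm: 0 of 5.

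The imbalance against each comparator is therefore 4 − 0 = 4 visits, all of the follow-up.

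**What cannot be computed.** The documents give no size for a removal effect and no size for any strength gain lost when tape comes off. Section 6 gives a sample size but no effect size, standard deviation, alpha or power. No change in power or in the estimated difference can be derived, and none is offered here.

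**Other data on tape in use.** All arms keep a daily symptom journal, which covers days of wear, and the Section 9 interview asks intervention participants about wearing the tape. Section 11 assigns the interviews and journals to Objectives 2 and 3 and names neither for Objective 1.

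**The case against.** The best case for the plan is that testing off tape is a legitimate choice. Baseline is off tape and Section 11 analyses change from baseline, so off-tape follow-up compares like with like. Tape across the wrist and to the digits could itself alter grip and pinch mechanics, and testing with it on would set a taped hand against untaped hands in the other two arms. Section 16 also gives tape principles that are not purely positional (fluid flow and analgesia), and several days of a more open carpal tunnel could leave a benefit after removal. This stands for strength. What is missing is a statement that the residual effect is the target.

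Three stronger readings are tempting, and the documents do not support them.
- A reader might infer that the trial never observes tape in use. It does, through journals and interviews; the gap is confined to the Objective 1 outcomes.
- A reader might infer that ratings are made within minutes of peeling. Only the order is given. Splint checks and journal collection stand between removal and the forms, and the scripts and timeline are cited as appendices that are not in the text reviewed.
- A reader might infer that removal raises pain and lowers grip. Section 12 says "Participants may experience discomfort or skin irritation from wearing the tape, splint or completing the exercises", which concerns wearing, not removal, and it names removal as the response to such problems. On that text, removal could as easily bring relief.

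The pain and function forms may also use recall periods that cover days of wear. If so, they capture tape in use and a momentary removal effect matters less. The forms are not in the text, so this is open. It is a reason to regard the point as firmest for grip and pinch.

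Removal first might be defended as protecting masking, but Section 9 says the researchers know which intervention is under study, and the same staff group removes and re-applies the tape.

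**Conclusion.** The point holds as a matter of measurement order and interpretation. No Objective 1 outcome is scheduled with dorsal tape in place (0 of 5 visits), and at all 4 follow-up visits only the intervention arm has adhesive taken from the rated limb before rating. The plan states neither an interval nor a reason. This rests on reading the order of sentences in steps 9 to 12 as the order of events, which the placing of re-application after the measurements supports.

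The documents do not show a bias of any given size or direction, and off-tape strength testing is not in itself an error. The case for change is that an arm-specific procedure stands before subjective ratings without need, and that the strength result, as planned, answers a narrower question than Objective 1 appears to ask.

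**What to change.** In steps 9 to 12, have participants in all three arms complete the Numeric Pain Rating Scale, the Visual Analogue Scale and the Boston questionnaire on arrival, before any tape is removed or splint checked. This changes only the order of existing tasks. It adds no visit, form or time, and at most needs matching edits to the visit scripts.

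Grip and pinch may stay after removal, matching the off-tape baseline. In that case add a sentence to Sections 8b and 11 saying that the strength comparison concerns the residual effect after tape removal, not the effect of tape in use, and report it in those terms. If an interval between removal and testing is intended, write it into the steps.

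A tape-on grip and pinch measurement is optional. It would take a few extra minutes and would compare taped with untaped hands, so if added it should be labelled as a separate measure of tape in use.
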